Methods and Analysis: This will be a single center prospective before-and-after proof-of-concept study. Adults (18 years and older) undergoing elective surgery and recovering in two selected PACU bays will be enrolled. During the initial 3-month observation phase, clinicians in the telemedicine center will not communicate with clinicians in the PACU, unless there is a specific patient safety concern. During the subsequent 3-month interaction phase, clinicians in the telemedicine center will provide structured decision support to PACU clinicians. The primary outcome will be time to PACU discharge readiness determination in the two study phases. The attitudes of key stakeholders towards the telemedicine center will be assessed. Other outcomes will include detection of physiological derangements, complications, adverse symptoms requiring treatments, and emergencies requiring medical intervention.

Registration Information: This trial is registered on clinicaltrials.gov, NCT04020887

Keywords:

Telemedicine, Post-Anesthesia Care Unit, Protocol, Proof-of-Concept, Observational Study

Introduction

After invasive procedures in the operating room (OR) or other procedure rooms, patients are usually transferred to a post-anesthesia care unit (PACU) for high acuity monitoring. The PACU period is important for patients, especially since they often are still in a vulnerable state.^{1,2} Patients are prone to peri-procedural and post-anesthetic complications including dehydration, anemia, coagulopathy, bleeding, hypothermia, delirium, respiratory depression, airway obstruction, bronchospasm, hypotension, kidney injury, arrhythmias, metabolic acidosis, hypoxemia, glucose and electrolyte abnormalities, atelectasis, and pulmonary edema.^{3,4} These complications must be recognized and appropriately managed by PACU clinicians. Furthermore, PACU clinicians need to identify and manage patients' adverse symptoms including pain, nausea, urine retention, weakness, and itching, which are common after invasive procedures, whether with or without general anesthesia.

The ideal PACU environment provides close monitoring and prompt rescue for peri-procedural complications, while also efficiently transferring patients to their next phase of care. For example, when patients deteriorate in the PACU, it is important to recognize this early, intervene appropriately, and arrange transfer to a higher acuity area, such as an intensive care unit, when warranted.

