In the first three months (the Observation phase) of this proof-of-concept study, a telemedicine center for the PACU will monitor patients assigned to two PACU bays. Both the telemedicine center and nurses caring for patients in the PACU bays will separately document physiological derangements (Table 2), treatable symptoms (Table 3), or a situation requiring urgent medical intervention (telemedicine center only; Table 4) during the PACU stay. Clinicians in the telemedicine center will assess when the patient meets discharge criteria, based on the modified Aldrete scale¹⁵ and their clinical judgment. They will document the time that discharge criteria are met, the modified Aldrete scale score at this time, and any additional relevant information. If clinicians in the telemedicine center judge that they are unable to determine a patient's readiness for discharge, they will document their reasons (Table 5). Clinical judgment will be used in determining appropriate discharge parameters for patients with pre-existing conditions. The telemedicine center clinicians will document each patient's information outlined in Tables 2-5 directly into REDCapTM (a secure web application for managing online surveys and databases) and AlertWatch. After a patient has been discharged from the PACU, the PACU nurse will fill out a form providing information outlined in Tables 2-5. This includes

information on physiological derangements, treatable symptoms, and discharge information. This form will be collected by the research team, and the information in the form will be documented in REDCap. During this phase of the study, clinicians in the telemedicine center will not communicate with clinicians in the PACU (nurses or physicians), unless there is a patient safety event.

Table 2. Physiological derangements and complications

Did the patient have any of the following physiological derangements:	Definition: (for study purposes)
Persistent confusion / delirium	
Tachycardia	HR >120/min
Bradycardia	HR <45/min
New onset atrial fibrillation	
Respiratory depression	<8 respirations per minute
Hypoxemia	<90% O ₂ Saturation
Hypotension	MAP <55
Weakness	<5/5 power in limbs
Emesis / vomiting	
Hyperglycemia	Glucose >200mg/dL
Hypothermia	Temperature < 35.5 C
Low urine output (for PACU stay >4h)	<0.5 ml/kg per hour

Table 3. Symptoms requiring treatment

Did the patient complain of the following symptoms:	
Dizziness or lightheadedness	Difficulty breathing
Nausea	Shivering

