Physiological derangements – Success will be measured (in the observation phase) by the ability of the telemedicine center clinicians to identify physiological derangements as they are occurring in the PACU. The extent to which the telemedicine center clinicians can identify these physiological derangements will be measured by comparing PACU nurse and telemedicine center assessment surveys for each patient (Figure 3).

Symptom identification and management – Success will be measured (in the observation phase) by the ability of the telemedicine center clinicians to identify treatable symptoms as they arise in the PACU. The extent to which the telemedicine center clinicians can identify these treatable symptoms will be measured by comparing PACU nurse and telemedicine center assessment surveys for each patient (Figure 3).

Emergency situations – Success will be measured (in the observation phase) by the ability of the telemedicine center clinicians to identify situations requiring emergency medical intervention as they are occurring in the PACU. By construction, any time the telemedicine center feels that an emergency situation is present, preserving patient safety mandates contacting the bedside clinician.

During each such contact, the telemedicine center clinician will ask if the PACU nurse was already aware of the situation, disagreed with the assessment, and had already spoken to the supervising physician regarding it. The occurrence of emergency medical situations will be extracted from the electronic health record, and the agreement between telemedicine center and PACU nurse assessments will be quantitated.

PACU discharge – Success will be measured by the ability of the telemedicine center clinicians to identify when patients are ready for discharge (observation phase [without communication] and interaction phase [active communication with patient and PACU clinicians]) (Figure 3). The impact of the telemedicine center on this key function will be examined based on feedback from key stakeholder focus groups (interaction phase; see *Aim 2*). The difference between sign-out times in the observation and the interaction phases will be compared.

Data collection methods and measures during the interaction phase

Aim 1: Demonstrate the potential utility of a telemedicine center for the PACU, to assist with PACU functions

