We will conduct focus groups with stakeholders to gain insights regarding their perceptions of barriers and facilitators related to the above-noted PACU functions before and after the implementation and use of a telemedicine center for the PACU. We will also gather perspectives from the stakeholders on the role and impact of the telemedicine center on their individual and team workflows in the PACU and between units during care transitions. Focus group participants will include nurses, anesthesiologists, surgeons, hospital administrators, and PACU telemedicine center clinicians. Our focus groups will be homogeneous in order to understand the clinician workflow based on their professional role, and their use of the telemedicine center in supporting their role and responsibilities. Each focus group will comprise five to six participants. This will allow in-depth discussions of the workflow problems and unintended

consequences caused by the implementation and use of the telemedicine center for the PACU. The focus group sessions will be guided by a semi-structured interview guide focused on the following themes: (1) PACU core functions, (2) PACU patient workflow, (3) PACU clinician activities and tasks, (4) tools and technologies used to support the PACU workflow, (5) major barriers to PACU functions, (6) use of a telemedicine intervention as a potential mechanism to support effective and efficient functioning of the PACU. We plan to conduct 6-8 focus group sessions (4 pre-intervention during observation phase, and 4 post-intervention during interaction phase) or until data saturation is attained.

Study Size

Patients are allocated to PACU bays according to the discretion of the nurse in charge of the PACU. Currently, approximately two patients per day are cared for in each bay in the participating PACU. Therefore, the telemedicine team will monitor approximately four patients per day over the course of the proof-of-concept study. We estimate that 500 patients will be included in this proof-of-concept study (250 per monitored phase) (Figure 4).

[figure not shown]

Figure 4. Allocation of sample size and PACU layout for proof-of-concept study

Statistical Methods

Primary Outcome

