This is a proof-of-concept study and will only address surrogate outcomes. The primary outcome (time to PACU discharge readiness) will use two comparison groups. First, historical controls will be drawn from the observation phase. A propensity score for inclusion into the study will be generated as a function of (minimally) surgery performed, day of week, time of day, age, and sex. 3:1 matched control patients will be included. The outcome will be analyzed with interrupted time series methods with flexible functions of calendar time used to adjust for secular trends; the study hypothesis is a non-zero discontinuity at telemedicine implementation.

That is, if Y_i is the outcome for the i th patient at time t_i with covariate vector X_i , while the implementation time is t_0 , and $I()$ is the indicator function,

$$Y_i = f_1(t_i)I(t_i < t_0) + f_2(t_i)I(t_i \geq t_0) + X_i\beta + \epsilon H_0: f_1(t_0) = f_2(t_0)$$

where f_1 and f_2 are smooth functions. Other patient factors known to strongly influence PACU length of stay (age, ASA physical status, number of co-morbidities, morbid obesity, obstructive sleep apnea, surgical specialty, primary anesthesia type, history of postoperative nausea and vomiting, preoperative pain, and scheduled case duration) will be included as covariates. The minimization criteria will be least squares or trimmed least squares or other robust criteria if there are substantial outliers. Outcomes will be examined for residual auto-correlation, and if non-negligible, auto-correlation robust standard errors (such as Newey-West errors) and an ARIMA model will be reported. Confidence intervals will be generated by non-parametric bootstrap sampling where possible. No adjustment will be made for matching, but bootstrap methods will respect the matched “units.” P-values will be generated both by likelihood ratio tests and by using non-deployment times as a null distribution; that is, we will run the same analysis looking for discontinuity at times remote from the true implementation time. We will conduct sensitivity analyses with transformations of the outcome variable. We will use an excluded run-in period of 1 month as a sensitivity analysis. Because hospital length of stay is unlikely to be meaningfully affected by a telemedicine center for the PACU, but does track overall acuity and surgical severity, we will use hospital length of stay as a control time series.

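### The stated power is for a difference in means, but the primary test is a jump at implementation, and the text does not say which bays supply the 3:1 historical controls

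*Combined protocol and SAP*

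**What the plan says.** **Test and precision (Statistical Methods, Primary Outcome).** The outcome is modelled with one smooth function of calendar time before implementation (t0) and another after it, plus covariates. The null hypothesis is f1(t0) = f2(t0). No degree or degrees of freedom are given for the trends. The same section gives a mean of 150 min and SD of 65 min, then claims more than 90% power at alpha 0.05 and more than 70% at 0.005 for a 20-minute fall in the mean with 250 patients per phase. It adds a bootstrap standard error (SE) of 5.5 min for a difference in means with 3:1 controls. It accepts that trend or covariate adjustment will raise this to some extent, and concludes that differences of 20-25 min can be resolved.

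**Control pool.** The text says "First, historical controls will be drawn from the observation phase", matched 3:1, with no adjustment for matching. It names no bays; Figure 4 (sample allocation and PACU layout) is not shown and might. The wording points two ways:

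- *Towards study-bay controls.* The Abstract says "The primary outcome will be time to PACU discharge readiness determination in the two study phases". In the Observation Phase section, "a telemedicine center for the PACU will monitor patients assigned to two PACU bays". Under the PACU discharge measure of success, "The difference between sign-out times in the observation and the interaction phases will be compared". The power statement also uses 250 per phase.
- *Towards other-bay controls.* "A propensity score for inclusion into the study will be generated as a function of (minimally) surgery performed" and other factors. Such a score presumes a pool of non-study patients, yet Study Size counts both phases as included: "We estimate that 500 patients will be included in this proof-of-concept study". The sensitivity model's indicator T, which marks study patients, implies the same.

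Study Size also says "Patients are allocated to PACU bays according to the discretion of the nurse in charge of the PACU".

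**The concern.** The power statement and the hypothesis concern different quantities. A jump between two separately fitted trends is estimated at the edge of each phase, where a fitted curve is least precise, so it needs far more data than a difference in phase means. If the SAP is taken at face value, a null jump could be misread as showing no effect.

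The control pool decides what the jump measures. With study-bay controls the stated ratio is not attainable from distinct patients. With other-bay controls the mix of bays changes at t0, the same moment as the intervention.

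**Working it through.** **Assumptions.** SD 65 min (from the SAP), patients evenly spread over each phase, two-sided tests, normal approximation. The linear trend form and any covariate R2 are mine.

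**1. Reproducing the plan's power.** SE = 65 × sqrt(1/250 + 1/250) = 5.81 min. Power for 20 min is Phi(20/5.81 − 1.96) = 93.1% at alpha 0.05 and 73.7% at 0.005. Both claims are met for a simple difference in means.

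At 250:750, SE = 65 × sqrt(1/250 + 1/750) = 4.75 min. The plan's 5.5 min would imply SD 75.3 at those numbers. The plan gives no n for it, so I also carry 5.5 forward.

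**2. The planned jump.** With a straight line on each side, SE = 65 × sqrt(4/n1 + 4/n2), exactly twice the SE without trends.

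| Pre : post | R2 | SE (min) | Power, 20 min | Power, 25 min | Difference at 80% power (min) |
|---|---|---|---|---|---|
| 250:250 | 0 | 11.6 | 41% | 58% | 32.6 |
| 750:250 | 0 | 9.5 | 56% | 75% | 26.6 |
| Plan's 5.5, doubled | 0 | 11.0 | 44% | 62% | 30.8 |
| 250:250 | 0.3 | 9.7 | 54% | 73% | 27.3 |
| 750:250 | 0.3 | 7.9 | 71% | 88% | 22.3 |

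R2 enters as sqrt(1 − R2). Quadratic trends triple the simple SE: at R2 = 0, power for 20 min is 21% (250:250) or 29% (750:250).

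**3. Study-bay controls.** Matching 250 interaction patients 3:1 needs 3 × 250 = 750 controls. Study Size says "Currently, approximately two patients per day are cared for in each bay in the participating PACU": 2 bays × 2 = 4 a day, or 4 × 5 × 13 = 260 on weekdays to 4 × 92 = 368 every day; 250 are planned. Without reuse only 250/3 = 83 patients could be matched fully.

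The documents do not mention reuse. If each of 250 controls were used three times, the model would report SE 9.5 against a true 11.6, a ratio of sqrt(1/250 + 1/750)/sqrt(2/250) = 0.816. The nominal 5% likelihood ratio test would then reject 2 × (1 − Phi(1.96 × 0.816)) = 11.0% of the time. Simulation gives about 11% for even and 14% for random reuse. A bootstrap over matched sets that share controls covers about 88%, not 95%.

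**4. Other-bay controls.** Let b be the study-bay minus other-bay difference left after matching and covariates.

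- If only other-bay patients precede t0, the jump is effect + b.
- If 750 other-bay patients are pooled with 250 observation-phase study-bay patients, the jump is effect + (750/1000) × b = effect + 0.75b.

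For illustration only, a true −20 with b = +10 gives −10 or −12.5; with b = −10 it gives −30 or −27.5.

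**5. The single T.** Take 250 study-bay and 750 other-bay patients in each phase, with T marking study patients in both. A true effect of −20 with b = 0 is split into a jump of 0.25 × (−20) = −5 and T = 0.5 × (−20) = −10. Neither is the effect. At b = +10 the jump stays −5 and T becomes 0.

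**The case against.** **Precision.** The power arithmetic is right for what it computes, and the 5.5-minute SE suits the separate contemporaneous t-test. The SAP warns that adjustment will enlarge the SE. Its covariates are chosen as strong predictors of PACU stay, and with R2 of 0.3 at 750:250 the 80%-power difference is 22.3 min, inside the claimed range. The claim of resolving 20-25 min might also mean only that an observed jump of that size would exclude zero; the half-widths are 1.96 × 9.49 = 18.6 and 1.96 × 11.63 = 22.8 min. All of that stands. However, a true difference equal to the half-width has only 50% power, no R2 is stated, and a doubling is not a modest increase.

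**Controls.** A reader might infer four stronger things that the documents do not support.

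- *That the primary p-values are invalid.* The SAP also plans a p-value using non-deployment times as the null distribution. In a reuse simulation with 22 placebo cut times (an assumed number) it rejected at most 4.9%. Only the likelihood ratio p-value and the matched-set interval are too optimistic, and only if controls are reused.
- *That neither control pool is workable.* The other-bay analysis can be run; its bias has unknown size and sign and could be small.
- *That the contemporaneous t-test carries the identical bias.* It matches on calendar time and is not covariate-adjusted, so the residual differs. Only a location or staffing component is shared.
- *That power lies between 41% and 56%.* That holds only for linear trends, R2 of zero and those two sample sizes. With 83 controls it would be 23% (SE 16.5).

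Hospital length of stay as a control series could flag an acuity shift at t0, but not a location or staffing difference. The limitations section disclaims causal attribution; that does not define the comparison group.

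**Conclusion.** The precision point holds: the stated power and SE do not apply to the planned discontinuity test. On linear trends, SD 65 and R2 of zero, power for 20 min is 41% (250:250) to 56% (750:250), against a claim of more than 90%. R2 of 0.3 would raise this to 54% and 71%, and more flexible trends would lower it. The trend form and R2 are assumptions because the plan gives neither.

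The control-pool point holds for the text, subject to Figure 4. With study-bay controls, 3:1 is impossible without reuse. With other-bay controls, the tested jump includes all, or about 75%, of any residual bay difference, and a T marking study patients in both phases does not isolate the effect. The documents do not show that such a difference exists. This should be fixed before analysis; confidence is medium.

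**What to change.** 1. **Precision.** Restate SE, power and resolvable difference for the model to be fitted, giving the assumed trend form and R2. State that a null jump will not be read as evidence of no effect.
2. **Control pool.** Name the bays and say whether controls may be reused.
3. **If study-bay controls are meant,** drop 3:1 and compare all observation-phase with all interaction-phase study-bay patients, using the covariates already listed.
4. **If other-bay controls are meant,** keep study-bay patients from both phases and match other-bay controls in both. In the sensitivity model replace the single T with gamma × S + delta × S × I(t ≥ t0), where S marks a study bay. Report delta beside the study-bay-only discontinuity.

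**Cost.** Items 1 to 3 are wording. Item 4 also needs an EHR pull of controls for both phases, with no change to conduct. Delta assumes a shared calendar trend and no spillover to other bays, and it is an average bay-by-phase difference, not a jump at t0. With an assumed 250 study-bay and 750 other-bay patients per phase, its SE is 65 × sqrt(2/250 + 2/750) = 6.7 min (85% power for 20 min). Scaled by 5.5/4.75 to the plan's SE it is 7.8 min (73%). Bay-specific linear trends double 6.7 to 13.4 min (32%), so the gain in power depends on the shared-trend assumption.

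### Day of week, time of day and sex help select the matched controls but are not named in the primary time-series model; naming them there guards against leftover imbalance at almost no cost

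*Combined protocol and SAP*

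**What the plan says.** All of this is in Statistical Methods, Primary Outcome.

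- **Matching.** The propensity score for historical controls has a stated minimum content: "minimally) surgery performed, day of week, time of day, age, and sex". Three controls are matched per study patient. The score for contemporaneous controls lists calendar time in place of day of week.
- **Outcome model.** The interrupted time series model has one smooth function of calendar time before implementation and another after it, plus a covariate vector X. The contents of X are introduced as "Other patient factors known to strongly influence PACU length of stay" and listed as "age, ASA physical status, number of co-morbidities, morbid obesity, obstructive sleep apnea, surgical specialty, primary anesthesia type, history of postoperative nausea and vomiting", then "preoperative pain, and scheduled case duration) will be included as covariates". Day of week, time of day and sex do not appear.
- **Use of the matching.** "No adjustment will be made for matching, but bootstrap methods will respect the matched" units. On intervals: "Confidence intervals will be generated by non-parametric bootstrap sampling where possible".
- **Other safeguards.** Residual autocorrelation is examined and, if it matters, met with Newey-West type errors and an ARIMA model. P-values come from likelihood ratio tests and from re-running the analysis at times away from implementation.
- **Sensitivity model.** A second time-series model pools historical and contemporaneous controls, adds an indicator for study patients and uses the same X.

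**The concern.** The plan treats weekday, clock time and sex as important enough to choose controls by, yet does not list them among the variables that adjust the outcome. For clock time the documents themselves suggest a mechanism. The Introduction says coverage and oversight differ between PACUs and within one PACU during a day. Table 5 defines the nurse's readiness time as the moment the anesthesiologist is called, which may depend on who is free. The Study Size section leaves bay allocation to the charge nurse, so study patients and other patients may differ in ways that vary with the hour.

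Two things are at stake. If imbalance in these variables remains after matching and differs around the implementation date, the model has no term to remove it from the estimated jump. And whatever outcome variance they explain stays in the residual.

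The pooled sensitivity model has a further gap. Day of week is not a named matching variable for the contemporaneous controls and is not in X, so for them it may be handled explicitly at neither step.

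**Working it through.** **1. Compare the two lists.**

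| Propensity variable (historical controls) | Named in X? |
|---|---|
| Surgery performed | Only as surgical specialty |
| Day of week | No |
| Time of day | No |
| Age | Yes |
| Sex | No |

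The qualifier for a minimum set belongs to the propensity score, not to X. Smooth functions over a six-month study cannot stand in for a weekly or daily cycle.

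**2. Reproduce the plan's figures.** Inputs from the Primary Outcome section: SD 65 min, 250 patients per phase, difference 20 min, bootstrap standard error (SE) 5.5 min. Sidedness is not stated; two-sided is assumed.

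- SE of a simple difference = 65 × √(2/250) = 5.81 min.
- Power at 0.05 = Φ(20/5.81 − 1.96) = 93.1% (plan: above 90%).
- Power at 0.005 = Φ(20/5.81 − 2.81) = 73.7% (plan: above 70%).
- Interval width = 2 × 1.96 × 5.5 = 21.6 min (plan: 22).

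The plan's figures reproduce.

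**3. Precision from adding the three variables.** Let R² be the share of residual variance they explain. The documents give no value, so 1-10% is assumed. The residual SD becomes 65 × √(1 − R²), and the SE of 5.5 becomes 5.5 × √(1 − R²).

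| Assumed R² | SE (min) | 95% interval width (min) | Power at 0.05 | Power at 0.005 |
|---|---|---|---|---|
| 0 | 5.50 | 21.6 | 93.1% | 73.7% |
| 1% | 5.47 | 21.4 | 93.3% | 74.2% |
| 5% | 5.36 | 21.0 | 94.2% | 76.5% |
| 10% | 5.22 | 20.4 | 95.2% | 79.4% |

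The SE falls by 1 − √0.99 = 0.5% up to 1 − √0.90 = 5.1%. The power columns use the plan's 250-per-phase comparison of means, not the full time-series model.

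**4. Residual imbalance.** Let d be the standardized imbalance that remains in the combined effect of the three variables. In a simple comparison of means, bias = d × √R² × 65. Values of d from 0.05 to 0.20 are assumed. The last column is the type I error of a nominal 5% two-sided test with SE 5.5.

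| R² | d | Bias (min) | Type I error |
|---|---|---|---|
| 1% | 0.05 | 0.3 | 5.0% |
| 1% | 0.10 | 0.7 | 5.2% |
| 5% | 0.10 | 1.5 | 5.8% |
| 10% | 0.10 | 2.1 | 6.6% |
| 10% | 0.20 | 4.1 | 11.6% |

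The last row needs both assumptions at their upper limits. Against the 20-min target, 4.1 min is about a fifth (4.1/20 = 0.21).

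**The case against.** **The variables may be intended already.** The list opens with the word other, directly after the propensity variables are given, and X is written generically. Weekday and clock time are not patient factors, so a list of patient factors need not contain them. This stands to the extent that nothing is expressly excluded. It does not settle the matter, because age is in both lists and surgical specialty overlaps with surgery performed, so the list is not simply the remainder. When the plan means to adjust for sex, as in the hand-off logistic model under Secondary Outcomes, it says so.

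**A reader might infer that the analysis ignores the matching.** The documents do not support that. The sentence disclaiming adjustment goes on to say that the bootstrap respects matched units, and the bootstrap is the default for intervals. Only the likelihood ratio p-value is not said to use matched sets. In a simple 1:3 comparison with within-set correlation ρ, the true variance is (1 − ρ) times the unmatched one. A nominal 5% test would then run at 4.4% for ρ = 0.05 and 1.9% for ρ = 0.3 (assumed values), which errs toward caution. Nor is the matching wasted: it aims at balance whether or not its inputs re-enter the model.

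**A reader might infer that weekly and daily cycles leave serial correlation untreated.** They do not. Robust errors, ARIMA and the placebo-time p-values are all planned.

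**A reader might infer that imbalance passes directly into the primary estimate.** The tested quantity is a jump at implementation, and these cycles recur on both sides of it. They bias the jump only if their mix differs around that date after matching on the same variables. The documents give no sign that it does; they also do not rule it out.

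**The gain may be nil.** The plan expects a somewhat larger SE once covariates or secular trends are adjusted for, and X already contains case duration and anesthesia type, which may overlap with clock time. This stands: no figure in the documents establishes a precision gain. The documents also offer no support for weekday or sex as predictors beyond their place in the score.

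**Conclusion.** The point holds as a minor, low-cost improvement. The primary outcome model, as listed, lacks three of its own matching variables, and no other term in it captures them. What is affected is the point estimate, through possible leftover imbalance, and the residual variance. The interval method and the handling of autocorrelation are not.

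Protection against imbalance is the main reason to act: 0.3 to 4.1 min of bias avoided over the assumed ranges (R² 1-10%, d 0.05-0.20), the upper end being unlikely because it takes both limits at once. The precision gain is possible and modest: SE about 0.5-5% smaller, and power at 0.05 at most about 95.2%. Both sizes rest on assumptions, since the documents give neither the variance explained nor the balance achieved. A reader should not conclude that the sample size or stated power is wrong; those figures reproduce.

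**What to change.** State that all propensity variables enter X in both the primary interrupted time series model and the pooled sensitivity model. Name day of week (categorical), PACU arrival time (smooth or categorical) and sex explicitly. For surgery performed, state the level of grouping used in X, since specialty is coarser than the matching variable and a finer grouping would use more terms.

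The cost is a few degrees of freedom: at most six for weekday, one for sex and a small number for arrival time. No new data are needed, because the matching already requires these variables. Fixing the list in advance also removes a discretionary choice from the primary analysis.
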